4.9.7 Safety MRI

Clinical assessments from the safety MRI will be summarized by descriptive statistics at each visit by treatment group. Radiographic hydrocephalus cases will be listed.

5. ANALYSIS OF OFF-TREATMENT FOLLOW-UP DATA

Following the recommendation from the iDMC to halt dosing in Study BN40423, patients entered the off-treatment follow-up period to monitor their safety and efficacy endpoints after the treatment discontinuation. This section describes the statistical analyses that will use data collected after treatment termination.

5.1 MIXED MODEL REPEATED MEASUREMENTS

Data collected up to Week 101 will be analyzed by an MMRM model as defined in Section 4.4.2. Different approaches will be defined for these MMRM analyses:

1. ITT analysis will include all patients in the ITT population
2. iDMC ad-hoc completer analysis will include patients who completed Week 101
3. Completer analysis will include patients who completed Week 101 and who had their last dose of study drug more than 5 months (> 152 days) prior to their Week 101 visit

The statistical modeling will be applied to the following endpoints:

- cUHDRS and its individual components
- MRI (BSI data, annualized percentage change from baseline)
- cUHDRS and components for age and CAP subgroups (if number of patients in the subgroup is sufficiently large, especially for the completers analyses)

5.2 SLOPE ANALYSIS

All analyses will be limited to patients who 1) received their last dose of any study treatment within 3 months (3*28 days) before 22 March 2021 (the date when it was publicly announced to stop treatment in Study BN40423) and 2) have at least one measurement collected during the off-treatment period for the selected outcome.

The statistical modeling will be applied to the following endpoints:

- cUHDRS and its individual components
- MoCA

This analysis will consider two periods: the on-treatment period and the off-treatment follow-up period, in order to compare the different slopes.

Two different approaches will be applied to define those periods:

1. Cut-off at date of last study drug intake (on-treatment period up to date of last dose)
2. Cut-off at date of last study drug intake plus 5 months (on-treatment period up to date of last dose + 152 days)

A linear mixed effect model (LMM) will be performed using time as a continuous variable and including a random intercept and a random slope to investigate the treatment effect by comparing the slopes. Baseline age, CAP score, and CAG will also be included in the model.

- **Within Treatment Comparison While on Treatment Versus After Treatment Stop:**

Within each treatment, the rate of declining in clinical endpoints during the off-treatment follow-up period is compared with the rate of declining during the on-treatment period.

- **Between Treatment Comparison of the Slopes After Treatment Stop:**

The slope after treatment stop of the active treatment (individually per treatment schedule) will be compared with that of placebo group.

If the model fails to converge, the following steps might be adapted:

1. Relaxing the assumption of different variance of the random effect of change in slope for each treatment group
2. Excluding the random effect of change in the slope after treatment stop
3. Relaxing the assumption of different variance of the random slope for each treatment group

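### Restricting every slope analysis to patients with an off-treatment value can create a false steepening after treatment stop; the same model on all recently dosed patients should stand beside it

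*SAP*

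**What the plan says.** SAP Section 5.2 sets two conditions for all slope analyses. The patient must have "received their last dose of any study treatment within 3 months (3*28 days) before 22 March 2021" (criterion 1) and must "have at least one measurement collected during the off-treatment period for the selected outcome" (criterion 2). A patient who meets the first but not the second loses the on-treatment data as well.

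The model is stated thus: "A linear mixed effect model (LMM) will be performed using time as a continuous variable and including a random intercept and a random slope". A random change of slope appears only in the list of convergence fallbacks ("Excluding the random effect of change in the slope after treatment stop").

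Two contrasts follow. Within each arm, "the rate of declining in clinical endpoints during the off-treatment follow-up period is compared with the rate of declining" on treatment. Between arms, "The slope after treatment stop of the active treatment (individually per treatment schedule) will be compared with that of placebo group". Both are run with the off-treatment period starting after the last dose (cut-off 1) and again with it starting 152 days later (cut-off 2).

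Section 5.2 gives no reason for criterion 2, no missing-data assumption and no version without the restriction. Section 5.1, on the off-treatment MMRM, does keep a full ITT set beside two completer sets. Section 4.4.2 states missing at random for that MMRM. Section 2.4 calls the analysis of data after 22 March 2021 exploratory.

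**The concern.** Criterion 2 selects patients on something that happens after the halt: coming back. If patients whose scores had visibly worsened return less often, those who remain have an on-treatment slope that is too shallow, partly because their last on-treatment values were favourable by chance. Their later values regress to the mean, and the off-treatment slope looks steeper although nothing changed at treatment stop.

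Such an artefact could be read as worsening after drug withdrawal. If selective return differs by arm, it could be read as a difference between active drug and placebo. With no slope analysis on the wider set, a reader of the results could not see whether this had happened.

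**Working it through.** Section 5.2 states no figure, so there is none to reproduce. The check has three parts.

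**1. Does the model need criterion 2?** Write the score as b0 + b1·t + b2·(t − k)₊ plus a random intercept, a random slope, possibly a random change of slope, and error, with k the cut-off. A patient seen only before k still informs b0, b1 and the variance components. Under missing at random, that patient also corrects the fit for selective return. So the model does not need it.

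**2. Who can be lost?** Criterion 1 allows a last dose up to 84 days before 22 March 2021. The early treatment termination (ETT) visit is due within 56 days of the decision to stop (Section 2, Figure 1 footnote). Taking 22 March as that date, a timely ETT visit falls at most 84 + 56 = 140 days after the last dose. It can satisfy criterion 2 under cut-off 1 if the outcome is measured there. It cannot under cut-off 2, because 140 < 152. Cut-off 2 can therefore lose more patients. If criterion 2 is applied separately for each cut-off, the two approaches may analyse different patients.

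**3. How large can the effect be?** TFC stands in, because the SAP gives no variances for cUHDRS or MoCA. Inputs from Section 2.3: decline 1.36, SD of change 1.56 (Week 49) and 1.78 (Week 101), covariance 1.8. Check: 1.8/(1.56 × 1.78) = 0.648, as stated (0.65). Annual decline: 1.36/(101/52) = 0.70.

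*Simulation A.* For linear growth, Var(change at t) = s·t² + 2e and Cov = s·t₁·t₂ + e. With t = 49/101 and 1:
- s = (3.1684 − 2.4336)/(1 − 0.2354) = 0.96
- e = (3.1684 − 0.961)/2 = 1.10
- implied covariance = 0.961 × 0.485 + 1.104 = 1.57, against the stated 1.8

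Assumptions: mean slope -1.36 per 100 weeks; true change zero; visits at Weeks 1, 5, 21, 37, 53, 69, 85 and 101; cut-off at Week 69; SD 0.5 for the random change of slope; logistic return with log-odds 1 per SD of its driver; 40,000 patients, 3 replicates; maximum-likelihood fit. Results in TFC points per 100 weeks:

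| Return depends on | Return | Restricted: on / off / change | All: on / off / change |
|---|---|---|---|
| observed on-treatment change | 95% | -1.287 / -1.405 / -0.117 | -1.361 / -1.348 / +0.013 |
| same | 85% | -1.157 / -1.505 / -0.348 | -1.365 / -1.345 / +0.020 |
| same | 80% | -1.094 / -1.558 / -0.464 | -1.369 / -1.347 / +0.022 |
| same | 70% | -0.962 / -1.656 / -0.694 | -1.365 / -1.341 / +0.024 |
| true persistent slope | 85% | -1.238 / -1.192 / +0.047 | -1.357 / -1.094 / +0.263 |
| same | 70% | -1.108 / -1.117 / -0.008 | -1.349 / -0.911 / +0.438 |
| off-treatment change itself | 85% | -1.400 / -1.091 / +0.309 | -1.323 / -1.151 / +0.172 |
| nothing (random) | 85% | -1.355 / -1.363 / -0.008 | -1.355 / -1.363 / -0.008 |

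Multiplied by 0.52, the first four restricted changes are -0.06, -0.18, -0.24 and -0.36 per year. With 267 per arm the standard error is 0.33 to 0.38 per 100 weeks, and a nominal 5% test would reject in about 6%, 17%, 26% and 45% of trials. These are likely upper figures, since fewer than 267 per arm would meet criterion 1. Without a random change of slope, the 85% figure for observed-course return is -0.39.

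*Simulation B.* Slope variance 0.26 per year², error variance 0.87, truth -0.70 per year with no change at stop, odds of non-return 1.6 to 2.7 per SD of decline.
- Return by observed course, 18% non-return: false change about -0.10 to -0.26 per year restricted; at most about 0.03 in absolute value with all patients.
- The same at 5% non-return: at most about -0.07 restricted.
- Return by true slope, 18% non-return: about 0.01 restricted; +0.06 to +0.14 with all patients.
- Between arms, observed-course selection in the active arm only (cut-off 2, odds 2.7, about 17 to 18% non-return): restricted off-treatment slopes -0.83 and -0.70, a false difference of -0.13; about -0.01 with all patients.

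These components only approximate the SAP's matrix. With 48/52 and 100/52 years from Week 1, the SDs are √(0.26 × 0.852 + 1.74) = 1.40 and √(0.26 × 3.698 + 1.74) = 1.64, and the covariance is 0.26 × 1.775 + 0.87 = 1.33. A change-from-baseline model that matches all three entries gives roughly half the effect, -0.05 to -0.12 per year, in the same direction.

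**The case against.** A reader might infer that criterion 2 necessarily biases both planned contrasts and should simply be deleted. The documents do not support that.

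- **The bias depends on why patients return.** Random return produces none. If return follows the true persistent slope, the restricted set compares the same patients before and after stop and shows almost no false within-arm change, while the all-patient fit does. If return follows the off-treatment change itself, both fits are off. The near-zero all-patient result under observed-course return is expected, because that scenario is missing at random by construction.
- **The return rate is unknown.** The 20% and 15% in Section 2.3 are assumed treatment discontinuation, not failure to return. Criterion 1 keeps recently dosed patients, and under cut-off 1 the ETT visit can qualify, so loss may be small. At 5% non-return the distortion is minor against its standard error.
- **Some loss under cut-off 2 may be administrative.** The third set in Section 5.1 implies that some patients reach Week 101 without being 152 days past their last dose. Such loss need not relate to decline.
- **Context.** The analysis is exploratory, and Section 5.1 already covers cUHDRS and its components in the full ITT set.

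All of this stands, and it argues against deleting the criterion. It does not justify the restricted set alone. Section 5.1 gives neither slopes nor MoCA, and nothing planned would show which return pattern applies. The restricted set is also not safe between arms: under true-slope return its off-treatment slope is too shallow (about -0.61 to -0.66 against -0.70 per year), which matters if arms differ. The all-patient fit does not cure that case; in simulation A at 85% return its off-treatment slope is further from the truth (-1.094 against -1.192, truth -1.36).

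**Conclusion.** The point holds as a conditional one. Criterion 2 is not needed by the model, is unexplained and has no unrestricted counterpart. If return depends on the observed on-treatment course, it can create a false steepening of about -0.10 to -0.26 TFC points per year at 18% non-return (14% to 37% of 0.70: 0.10/0.70 and 0.26/0.70) and at most about -0.07 at 5%. Where that selection occurs in one arm only, it can also create a false between-arm difference, -0.13 per year in the case tried.

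These sizes rest on assumed return rates and selection strengths, on TFC as stand-in, and on variance components that only approximate the SAP's matrix; matching the matrix roughly halves the within-arm figure. Neither analysis set is right under every return pattern, so both should be reported.

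**What to change.** Amend Section 5.2 as follows:

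- Fit the same model to all ITT patients who meet criterion 1, using all their on-treatment data and any off-treatment data. State that this analysis assumes missing at random.
- Report it alongside the restricted-set analysis, for both cut-offs.
- Say which definition of the off-treatment period criterion 2 uses under each cut-off.
- Tabulate, by arm and cut-off, the proportion without off-treatment data, separating patients who had no visit scheduled after the cut-off from those who missed one.
- Show the on-treatment course of returners against non-returners, by arm and cut-off.
- Treat a change of slope at treatment stop as robust only if both sets agree.

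The cost is a short SAP amendment, one extra model run per outcome and cut-off on data already collected, and the added tables. The downside is that the all-patient result rests on missing at random, which can fail in the ways shown above; that is why the restricted set stays in the report.

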2.3 DETERMINATION OF SAMPLE SIZE

The planned sample size is adequate to capture meaningful clinical decline on both the TFC and cUHDRS and was estimated applying a meta-analysis on data available from non-interventional studies (TRACK-HD, COHORT, ENROLL-HD) and a randomized placebo-controlled study (2CARE). Results of the meta-analysis on the change from baseline at 24 months in TFC suggested a natural decline of 1.36 points and a corresponding pooled standard deviation of 1.78. A conservative treatment discontinuation rate at Week 101 for patients receiving placebo or active is assumed to be 20% and 15% respectively.

Using these assumptions, 267 patients per arm was estimated to provide approximately 80% power, at a two-sided ≤ 0.025 level, to detect a 40% slowing of clinical decline for RO7234292 as compared with placebo at 101 weeks. The proposed sample size was estimated based on simulations (further described below). The assumed treatment effect translates into an expected average decline of ~ 0.82 points at 101 weeks for the RO7234292 arms. The minimal detectable difference with these assumptions is ~ 0.38 points.

Given the above sample size, the cUHDRS, the more sensitive outcome measure, is powered at 80%, at a two-sided ≤ 0.025 level, to detect a 30% slowing of clinical decline for RO7234292 as compared with placebo at 101 weeks. Since there are presently no therapies available to stop or slow clinical progression in HD, any slowing of clinical progression of overall functional decline or linked overall functional, cognitive, and motor decline may be considered meaningful, such that between a 20%-40% slowing of decline, translating to approximately 2.5-4.5 months per year of time saved from progression, would represent a meaningful treatment effect.

Description of simulations to derive the sample size

The design used for the simulation was simplified to consider only 2 treatment arms (placebo and active) and 2 post-baseline time-points (Week 49 and Week 101).

1. The following algorithm was run and repeated 500000 times:
Generate change from baseline values in TFC at Week 49 and Week 101 for **N active patients** according to the following bivariate normal distribution:

$$\begin{pmatrix} y_{wk49} \\ y_{wk101} \end{pmatrix} = N\left(\mu = \begin{pmatrix} 0.47 \\ 0.82 \end{pmatrix}, \Sigma = \begin{pmatrix} 1.56^2 & 1.8 \\ 1.8 & 1.78^2 \end{pmatrix}\right)$$

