4.4 EFFICACY ANALYSIS

Given the date of the public announcement of the Sponsor halting dosing in Study BN40423 (following the iDMC recommendation), only data collected up to 22 March 2021 will be used to evaluate the efficacy of RO7234292 (to avoid any bias from data collected after the official announcement).

For all efficacy endpoints, the baseline will be defined as the last assessment on Day 1. Further reporting windows are defined in [Appendix 1](#).

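### Section 5.2 compares slopes within each arm and after stopping, but omits the active-minus-placebo difference in slope change

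*SAP*

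**What the plan says.** SAP Section 5.2 fits a linear mixed model with continuous time, a random intercept and a random slope. Its stated aim is "to investigate the treatment effect by comparing the slopes". It lists two comparisons:

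- Separately by arm: "the rate of declining in clinical endpoints during the off-treatment follow-up period is compared with the rate of declining during the on-treatment period". This covers the placebo arm as well as the two active schedules.
- Between treatments, "The slope after treatment stop of the active treatment (individually per treatment schedule) will be compared with that of placebo group".

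Both are run under two definitions of the on-treatment period, one ending at the last dose and one at the last dose plus 152 days. The first fallback step for non-convergence is "Relaxing the assumption of different variance of the random effect of change in slope for each treatment group", so the model already carries a change in slope by treatment group. Section 2.4 calls the analysis of data after 22 March 2021 exploratory. Section 5.2 sets no hypothesis, alpha level or decision rule.

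**The concern.** The question raised by splitting follow-up at the last dose is whether stopping changed the rate of decline more on active drug than on placebo. Neither listed contrast tests this.

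The within-arm contrast has no control. Off-treatment time is later time for every patient, so a disease course that is not linear, practice or placebo response early in the study, and altered expectation after the halt all fall into the same before-and-after difference. Section 5.2 identifies 22 March 2021 as "the date when it was publicly announced to stop treatment in Study BN40423", and Section 4.4 keeps later data out of the efficacy evaluation "to avoid any bias from data collected after the official announcement". The SAP thus accepts that the announcement may affect the measurements.

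The off-slope contrast has a control but looks at one period only. It does not account for where each arm's slope stood on treatment.

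At stake is how an active-arm slope change is interpreted. Under Section 3.2 the iDMC's revised scope is itself a comparison of the on-treatment and off-treatment periods, so the controlled form of that comparison is worth specifying.

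**Working it through.** Section 5.2 gives no sample size or power, so there is no figure of its own to reproduce. The check has two parts.

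**1. What each contrast can show.** Write the slopes as rates of loss, with A for active and P for placebo.

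- Within arm: A_off − A_on, and separately P_off − P_on.
- Off-slope: A_off − P_off.
- Missing: (A_off − A_on) − (P_off − P_on).

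Take placebo slopes of 0.86 on and 0.57 off (derived in part 2), a change of −0.29. The active values below are assumed, to show the logic.

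| Active on | Active off | Off-slope contrast | Active change | Difference in slope change |
|---|---|---|---|---|
| 1.20 | 0.57 | 0.57 − 0.57 = 0 | −0.63 | −0.63 − (−0.29) = −0.34 |
| 1.20 | 1.20 − 0.29 = 0.91 | 0.91 − 0.57 = 0.34 | −0.29 | −0.29 − (−0.29) = 0 |

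In the first row the off-slope contrast is null although active changed more than placebo. In the second it is not null although both arms changed equally.

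**2. How far the slope can move with no drug stopped.** The inputs are the TFC simulation inputs in SAP Section 2.3. The 24-month meta-analysis there "suggested a natural decline of 1.36 points". The placebo means are 0.79 at Week 49 and 1.36 at Week 101, the SDs 1.56 and 1.78, and the covariance 1.8. Consistency check: 1.8 / (1.56 × 1.78) = 0.648, which agrees with the stated correlation of 0.65.

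- Loss up to Week 49: 0.79 × 52/48 = 0.86 points per 52 weeks (0.79 × 52/49 = 0.84 if Week 49 is counted as 49 weeks).
- Loss from Week 49 to 101: 1.36 − 0.79 = 0.57 points per 52 weeks.
- Change: 0.57 − 0.86 = −0.29 (or 0.57 − 0.84 = −0.27), a fall of 33% (or 32%).

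The variance of the per-patient slope change, per 52 weeks, is (1.56² + 1.78² − 2 × 1.8) + 1.56² × (52/48)² − 2 × (1.8 − 1.56²) × (52/48) = 2.00 + 2.86 + 1.37 = 6.23. The SD is 2.50.

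Now give the active arm the same course as placebo, so that there is no drug effect. The SAP does not give the number of patients in the slope analysis, so n per arm is an assumption. By normal approximation, a two-sided 5% test of no slope change within the active arm rejects as follows:

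| n per arm | 50 | 100 | 150 | 200 | 267 |
|---|---|---|---|---|---|
| Week 49 = 48 weeks elapsed | 13% | 21% | 29% | 37% | 46% |
| Week 49 = 49 weeks elapsed | 12% | 19% | 27% | 34% | 43% |

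A simulation of 5000 runs (48 weeks) gave, at n = 100 and n = 200:

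- within-arm change: 22% and 37%;
- off-slope contrast: 4.7% and 4.4%;
- difference in slope change: 5.1% and 5.1%.

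**Precision.** The within-arm SE is 2.50/√n and that of the difference is 2.50 × √(2/n), a ratio of √2 = 1.41 with equal arm sizes and variances.

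**The case against.** The strongest reply is that the plan is not uncontrolled. The within-arm comparison is also made in placebo, so a shift shared by all arms would be visible there. The off-slope contrast is placebo-controlled and keeps its 5% level under a common course. Section 5.1 adds an MMRM to Week 101 with visit-by-treatment terms, and Section 4.4.2 gives the placebo-controlled Week 69 difference. All this stands. It narrows the point but does not remove it. Seeing one within-arm test significant and another not is no test of their difference, and the MMRM in 5.1 does not test whether the slope changed more on active than on placebo when dosing ended.

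It is also fair that the figures are illustrative. They are planning inputs for TFC in a simplified two-visit simulation, not estimates for the slope-analysis subset, for cUHDRS or for MoCA. Week 49 stands in for stop dates that differ between patients, and a change of 0.29 is small beside a per-patient SD of 2.50.

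Three stronger readings are tempting, and the document does not support them:

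- A reader might infer that natural course or the halt will be reported as a drug effect. The SAP nowhere says that an active within-arm result will be read alone.
- A reader might infer that a conclusion on reversibility of worsening rests on Section 5.2. The SAP states no such objective, and the analysis is exploratory.
- A reader might infer that the second definition, "Cut-off at date of last study drug intake plus 5 months", contradicts Section 4.4. Eligible patients had their last dose 0 to 84 days before 22 March 2021, so 152 − 84 = 68 to 152 days after the announcement do count as on-treatment. But 152 days is the SAP's on-treatment rule in Sections 4.9 and 4.9.2, and Section 5.3 uses it too. Section 2.4 assigns later data to this exploratory analysis, and the first definition already cuts at the last dose. There is no contradiction, and truncation at 22 March 2021 is not needed.

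**Conclusion.** The point holds as a gap in the list of contrasts. Section 5.2 aims at a treatment effect through slopes, but leaves out the one contrast that sets the slope change on active against that on placebo. Read by itself, a within-arm change in an active arm is not evidence about stopping the drug: on the SAP's own placebo TFC inputs the slope falls by about one third with nothing stopped, and with no drug effect the within-arm test would reject in roughly 20% to 37% of trials at 100 to 200 patients per arm.

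The percentages depend on the assumed n, on a break at Week 49 and on TFC as the example. The case for the missing contrast does not depend on them. The contrast removes natural course and announcement effects only as far as these are equal across arms. The SAP reports that the sponsor was unblinded at the halt and does not mention patients or raters in that sentence, so equality is an assumption.

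**What to change.** In Section 5.2, for each active schedule and for both cut-off definitions, add the active-minus-placebo difference in slope change (off minus on) with a 95% CI, and name it the main contrast for the effect of stopping. Keep the off-slope comparison with placebo, which answers a different and legitimate question. Label the within-arm changes descriptive and show each active arm beside placebo.

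The cost is one linear contrast of terms that the model already carries by treatment group, with no new data. The estimate is less precise: its SE is about 1.4 times that of the within-arm contrast with equal arm sizes and variances. On the TFC illustration the 95% CI half-width would be about 1.96 × 2.50 × √(2/100) = 0.69 points per 52 weeks at 100 per arm and 1.96 × 2.50 × √(2/200) = 0.49 at 200. The interval should therefore be reported as it stands, and a wide one not read as absence of an effect.
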